## **11.7. Reporting**

### **11.7.1. Reporting Requirements**

Each AE is to be assessed to determine if it meets the criteria for SAE. If a SAE occurs, expedited reporting will follow local and European regulations, as appropriate.

All AEs will be reported on the AE page(s) of the eCRF. It should be noted that the form for collection of SAE information is not the same as the AE eCRF. Where the same data are collected, the forms must be completed in a consistent manner. For example, the same AE term should be used on both forms. AEs should be reported using concise medical terminology on the eCRFs as well as on the form for collection of SAE information.

### **11.7.2. Serious Adverse Event Reporting Requirements**

If a SAE occurs, Sponsor is to be notified within 24 hours of awareness of the event by the investigator. In particular, if the SAE is fatal or life-threatening, notification to Sponsor must be made immediately, irrespective of the extent of available AE information. This timeframe also applies to additional new information (follow-up) on previously forwarded SAE reports as well as to the initial and follow-up reporting of Exposure in Utero cases.

For all serious AEs, the investigator is obligated to pursue and provide information to Sponsor in accordance with the timeframes for reporting specified above. In addition, an investigator may be requested by Sponsor to obtain specific additional follow-up information in an expedited fashion. This information may be more detailed than that captured on the AE case report form. In general, this will include a description of the AE in sufficient detail to allow for a complete medical assessment of the case and independent determination of possible causality. Information on other possible causes of the event, such as concomitant medications and illnesses must be provided. In the case of a subject death, a summary of available autopsy findings must be submitted as soon as possible to Sponsor.

It is the investigators responsibility to maintain an accurate and up to date record of all AEs/occurrences in patients participating in the clinical trial. This record, including details of nature, onset, duration, severity, outcome and any relationship to investigational medicinal product, should be noted in the patient s medical notes. It is the investigators responsibility to review all events occurring at their site and as such the investigator must ensure that the patients are not compromised. Any appropriate action must be taken to protect the patients whilst ensuring validity of the results. It is the investigator responsibility to report correctly and on time to the sponsor SAE and to answer to queries at time.

All SAE Form must be sent to the sponsor by fax or e-mail to:

AnticipSanté

[name]

E-mail: [[contact]](mailto:[contact])

### **11.7.3. Non-Serious AE Reporting Requirements**

Non-serious AEs are to be reported on the AE eCRFs, which are to be submitted to Sponsor.

### **11.8. Frequent AEs**

The most frequently reported AEs of ATO are specified in the SPC (See Appendix 12) and provided below:

The most frequent events related to ATO are those:

- Related to cardiovascular system (tachycardia, QT prolongation...)

Prolongation of the QT interval in the EKG has been observed during treatment with ATO. This can lead to ventricular tachycardia (*torsade de pointes*) with a fatal outcome. In this context, possible interaction with other drugs that prolong the QT interval must also be taken into account (see Appendix 7 for drugs reported to prolong QT interval and/or induce *torsade de pointes*).

For this reason, close monitoring of the EKG and of the electrolytes is necessary during treatment with ATO. In particular, the  $Mg^{++}$  and  $K^+$  levels should always be kept in the high-normal range, taking in consideration possible concomitant treatments that deplete electrolyte levels (e.g. amphotericin B, furosemide etc.). In the EKG, the QT interval is represented by the QRS complex, the ST segment and the T wave. Its measurement starts from the deepest point of Q wave to the end of T wave. This interval greatly depends on the heart rate and several formulas have been proposed to adjust the QT interval for heart rate in order to obtain the corrected QT interval (QTc); however, no one of these proposed formulas is satisfactory (Indik JH, 2006; Luo S, 2004; Sagie A, 1992). Despite that, data from medical literature indicate that one of the most simple method for adjusting the QT interval for heart rate is the Framingham formula (Indik JH, 2006; Luo S, 2004; Sagie A, 1992):

$$QTc = QT + 0.154 * (1000 - RR)$$

Using this formula, the upper normal limits of QTc interval calculated from the EKG of 10,303 subjects collected from 4 US hospitals (Luo S, 2004) are reported in the table below:

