#### **4.2 Exclusion criteria**

Patients fulfilling ONE or MORE of the following criteria will not be included in the study:

- Patient developing acute GvHD (whether early or “late onset” form)
- Patients developing overlap GvHD as defined by the 2015 NIH Working Group Consensus (presence of one or more acute GvHD manifestation in a patient with a diagnosis of chronic GvHD)
- A “mild” form of chronic GvHD not requiring systemic immunosuppressive therapy
- A “moderate” form of chronic GvHD limited to one organ site not requiring systemic immunosuppressive therapy
- Patient receiving mycophenolate mofetil
- Second allogeneic stem cell transplant
- Severe cardiac diseases (congestive heart failure (NYHA class III), recent myocardial infarction (in the past 6 months before the inclusion), histories of unexplained syncope, ...)

- Significant arrhythmias, EKG abnormalities:
  - Congenital QT syndromes
  - History or presence of significant ventricular or atrial tachyarrhythmia
  - Clinically significant resting bradycardia (<50 beats per minutes)
  - QTc > 450 msec for men and > 470 msec for women on screening EKG (using the QTcF formula, in Section 11.8)
  - Right bundle branch block plus left anterior hemiblock, bifascicular block
- Central or peripheral neuropathy
- Neutrophils <  $0.5 \times 10^9/L$
- Platelets <  $50 \times 10^9/L$
- Potassium  $\leq 4 \text{ mEq/l}^*$
- Magnesium  $\leq 1.8 \text{ mg/dl}^*$
- Calcium  $\leq 2.15 \text{ mmol/l}^*$
- Hepatic impairment due to a suspected or proven liver damage, other than direct hepatic cGvHD involvement
- PT < 50%
- Renal impairment (creatinine  $\geq 100 \mu\text{mol/l}$ )
- Uncontrolled systemic infection which in the opinion of the investigator is associated with an increased risk of the patients death within 1 month after the start of therapy
- Severe neurological or psychiatric disorders
- Denied informed consent
- Pregnancy
- Women breastfeeding at selection and throughout the treatment period

\* If abnormal at selection, to be corrected and re-validated following electrolytes infusion, before inclusion and each drug perfusion.

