### ECG and Electrolyte Monitoring Recommendations

During therapy with ATO, potassium concentrations must be kept above 4 mEq/l and magnesium concentrations must be kept above 1.8 mg/dl. In case of increase of QTc > 500 msec (Summary of Product Characteristics (Trisenox)), syncope, rapid or irregular heartbeat development, the treatment is immediately interrupted and the patient must be hospitalized, the EKG monitored continuously, serum electrolytes assessed and a cardiological advice requested.

ATO therapy must be discontinued until the QTc interval regresses to below 460 msec, electrolyte abnormalities are corrected, the syncope and irregular heartbeat cease. In accordance with the Safety Committee, the treatment could be reinitiated after the validation of the posology.

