### 8.2. Evaluations during treatment with ATO

The following evaluations must be performed:

- Before each administration of ATO during the first and the second cycle (if applicable):
  - Physical examination, including vital signs
  - EKG with measurement of the QTc interval according to the formula in Section 11.8
  - Serum chemistries: calcium, potassium, magnesium, creatinine
  - Collection of whole blood (5 mL) for pharmacokinetic assessment (see Section 8.4)
- At time of treatment initiation each week (for example days 1, 8, 15 and 24):
  - Physical examination, including vital signs, weight
  - GvHD assessment
  - Monitoring and recording of treatment associated, particular attention must be paid to drugs reported to prolong QT interval and/or induce torsade de pointes (see Appendix 7)
  - EKG with measurement of the QTc interval according to the formula in Section 11.8
  - Serum chemistries: potassium, magnesium, creatinine, uric acid, total bilirubin, alkaline phosphatases, LDH, total protein, albumin, SGOT (ASAT) and SGPT (ALAT) (twice a week), calcium, glycaemia (twice a week)
  - Hematology: complete blood count (CBC) with differential counts (twice a

week)

- Coagulation test with measurement of PT and APTT (twice a week)
- Infectious disease surveillance: CMV, EBV as per centre practice (and Hep B surface Ag, Hep B surface antibody if relevant)
- Monitoring the kinetics of certain autoantibodies [antinuclear antibody (AAN), anti-neutrophil cytoplasmic antibody (ANCA)]
- Collection of whole blood (5 mL) for pharmacokinetic assessment (see Section 8.4)
- Collect of whole blood (35 mL) for immunological evaluations ((see Section 8.3)

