**Table 5. Upper Limits (98%, in msec) of Normal QTc for Framingham formula (Luo S, 2004)**

Heart Rate (HR)	MALE (5,420)	FEMALE (4,883)	BOTH (10,303)
All HR	454	461	457
HR < 60	455	463	459
HR 60 to 99	454	462	458
HR > 99	436	434	436

For increased accuracy, the QT interval should be measured on serial EKGs and several successive beats and averaged for each EKG. The averaged QT value obtained should be used in the above formula in which all measurement must be expressed in msec (i.e.: 0,500 sec=500 msec). Applying this formula, a QTc interval > 500 msec must be considered prolonged (Summary of Product Characteristics (Trisenox)).

- Related to hepatotoxicity: increase in serum bilirubin and/or SGOT and/or SGPT and/or alkaline phosphatase,
- Related to Hematological toxicity. This drug may induce severe and prolonged myelosuppression with subsequent anemia, neutropenia, thrombocytopenia. Less frequently hyperleucocytosis or leucopenia have been reported.
- Related to general tolerance (fever, chills, fatigue, bleeding, edema...)
- Related to immunosuppression such as infectious complications (candidosis, herpes-zoster, pneumonia, bacteremia, septicemia, septic choc...),
- Related to digestive toxicity (nausea, vomiting, diarrhea...),
- Related to metabolism disorders (hyperglycemia, hypokalemia, hypomagnesaemia...),
- Renal insufficiency,
- Related to nervous system (paraesthesia, dizziness, headache...),
- Related to eye disorder (vision blurred),
- Related to cutaneous tissues (prurit, rash...),
- Related to musculoskeletal, connective tissue and bone disorders (myalgia, arthralgia, bone pain...).
- Related to pulmonary disorders (dyspnea,,,)

All AE not previously described in the Summary of Product Characteristics of TRISENOX® or in the Investigator Brochure of ARSCIMED® should be considered as unexpected AE.

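### Protocol 11.8 starts the QT measurement at the lowest point of the Q wave, contradicting its own definition of QT; followed literally, it weakens the 500 and 460 msec arsenic trioxide rules

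*Protocol*

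**What the plan says.** Protocol section 11.8 contains two consecutive statements about the interval. The first is a definition: "the QT interval is represented by the QRS complex, the ST segment and the T wave". The second is a measuring instruction: "Its measurement starts from the deepest point of Q wave to the end of T wave". The section then gives the Framingham correction and, below Table 5, says that "the QT interval should be measured on serial EKGs and several successive beats and averaged for each EKG", with the averaged value entered in the formula.

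Other sections rely on this one:

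- Section 8.2 requires, before each infusion, an "EKG with measurement of the QTc interval according to the formula in Section 11.8".
- Section 4.2 sets the entry limits of 450 msec (men) and 470 msec (women) "on screening EKG (using the QTcF formula, in Section 11.8").
- The ECG and electrolyte monitoring text in section 7.3.2 interrupts treatment "In case of increase of QTc > 500 msec", and adds that "ATO therapy must be discontinued until the QTc interval regresses to below 460 msec".

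Nothing else in the two documents as supplied gives a different start point or corrects this one.

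**The concern.** The two statements cannot both be followed. The definition makes QT begin where the QRS complex begins. The instruction starts later, at a point inside the QRS complex, so it drops the stretch from QRS onset to the bottom of the Q wave. In a lead with no Q wave it gives no start point at all.

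QTc matters in this trial. Section 11.8 itself warns that QT prolongation under arsenic trioxide can lead to fatal torsade de pointes. Section 6.3 suggests or permits trimethoprim/sulfamethoxazole, inhaled pentamidine, fluconazole and itraconazole, and Appendix 7 lists all four among QT-prolonging drugs. Section 10.6 sets no study-level stopping criterion. For a patient without symptoms, the 500 msec limit is the only trigger in the interruption rule. A reading that is systematically short delays interruption, allows earlier restart and admits patients above the intended entry limits.

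**Working it through.** **Inputs.** From the protocol: the Framingham formula QTc = QT + 0.154 × (1000 − RR), in msec (11.8); interruption above 500 and restart below 460 (7.3.2); entry limits 450 and 470 (4.2); all-heart-rate upper normal limits of 454 for men and 461 for women (Table 5). Not in the documents: d, the time from QRS onset to the bottom of the Q wave. I assume 2, 5, 10 and 20 msec. The plan states no figure on this point to reproduce.

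**Step 1: effect on QTc.** With QT short by d,

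QTc read = (QT − d) + 0.154 × (1000 − RR) = true QTc − d.

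RR cancels, so the deficit is d at any heart rate. Check with a true QTc of 505 and d = 10:

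- 75 bpm (RR 800): QT = 505 − 30.8 = 474.2; the reading is 464.2 + 30.8 = 495.
- 50 bpm (RR 1200): QT = 505 + 30.8 = 535.8; the reading is 525.8 − 30.8 = 495.

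In both cases the interruption rule does not fire. Likewise, a true 465 reads 455 and meets the QTc condition for restart.

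**Step 2: effect of averaging.** If every beat is short by d, the mean of n beats is short by d for any n. Averaging reduces random reading error and leaves this deficit unchanged.

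**Step 3: effective limits, in true QTc (msec).**

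| d (assumed) | Interrupt above | QTc permits restart below | Entry limit, men / women (Framingham) |
|---|---|---|---|
| 0 | 500 | 460 | 450 / 470 |
| 2 | 502 | 462 | 452 / 472 |
| 5 | 505 | 465 | 455 / 475 |
| 10 | 510 | 470 | 460 / 480 |
| 20 | 520 | 480 | 470 / 490 |

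The scaling is linear; an extreme d of 40 would give 540 and 500 for the two treatment rules.

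**Step 4: entry limits if QTcF means Fridericia.** Section 4.2 names QTcF, while 11.8 prints only Framingham. If Fridericia was meant, QTcF = QT / (RR/1000)^(1/3), and the shift is d / (RR/1000)^(1/3):

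- 50 bpm (RR 1200): 0.94d
- 60 bpm (RR 1000): 1.00d
- 100 bpm (RR 600): 1.19d
- 120 bpm (RR 500): 1.26d

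For d = 10 that is 9.4 to 12.6 msec, in the same direction.

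**Step 5: restart limit against Table 5.** Table 5 gives "Upper Limits (98%, in msec) of Normal QTc for Framingham formula". With d = 0, 460 is 6 above the male limit (460 − 454) and 1 below the female limit (460 − 461). With d = 2, 5, 10 or 20, a reading of 460 is truly 8, 11, 16 or 26 above the male limit and 1, 4, 9 or 19 above the female limit. This assumes the table's source measured from QRS onset, which the protocol does not say; treat it as illustration only.

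**The case against.** The strongest reply is that the sentence sits in explanatory text under frequent adverse events, that sections 4.2 and 8.2 refer only to the formula there, and that the correct definition stands directly before the faulty sentence. Experienced readers and automated machines may well start at QRS onset regardless. The size is unsupported, since d appears nowhere and the table above restates an assumption. A patient must be within d of a limit for anything to change. Other barriers exist: hospitalisation at the start of treatment, an EKG and electrolytes before every infusion, interruption for syncope or irregular heartbeat, potassium and magnesium floors, cardiological advice, and Safety Committee agreement before restart. No efficacy analysis is touched. On the planned calendar (last visit June 2020; the SAP's response algorithm is dated 19 October 2020), a correction may come too late to alter dosing.

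Most of this stands as a limit on weight: the size is unknown, site practice is unknown, the window is narrow and the other safeguards are real. It does not remove the defect. The formula needs a measured QT, and section 11.8 is the only place that says how to obtain one. Having the right definition next to a contradictory instruction leaves the choice to each site. None of the other safeguards corrects the reading.

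**Conclusion.** The concern holds. Section 11.8 contradicts itself on where QT begins, and the measuring instruction is the wrong one of the two. The direction is certain for any d above zero: QTc reads low, and the interruption, restart and entry limits all become less protective. Under Framingham the shift equals d, so 2 to 20 msec over the assumed range. Three conditions limit the consequence: the site follows the sentence literally, the lead has a Q wave, and the patient lies within d of a limit. There is no evidence in the documents that any patient was affected. The effect on reported results is small, since the SAP shows QTc only among baseline characteristics (11.2.2) and omits it from the laboratory and physical examination tables (12.2, 12.3). It should be fixed because it bears on a drug-specific safety rule and costs almost nothing to correct.

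**What to change.** In Protocol 11.8, replace the measuring sentence with: *QT is measured from the beginning of the QRS complex to the end of the T wave.* This agrees with the section's own definition and also covers leads without a Q wave. Notify sites, and leave the 450/470, 460 and 500 msec limits unchanged. If dosing has already ended, correct the text before any reuse and state in the study report how QT was measured.

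The cost is one protocol sentence and a site notice. Slightly more readings will cross the existing limits, so a few more patients may be excluded, interrupted or restarted later. The mismatch between QTcF in 4.2 and the Framingham formula in 11.8 is a separate point that this change does not settle.

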**Table 5. Upper Limits (98%, in msec) of Normal QTc for Framingham formula (Luo S, 2004)**

Heart Rate (HR)	MALE (5,420)	FEMALE (4,883)	BOTH (10,303)
All HR	454	461	457
HR < 60	455	463	459
HR 60 to 99	454	462	458
HR > 99	436	434	436

For increased accuracy, the QT interval should be measured on serial EKGs and several successive beats and averaged for each EKG. The averaged QT value obtained should be used in the above formula in which all measurement must be expressed in msec (i.e.: 0,500 sec=500 msec). Applying this formula, a QTc interval > 500 msec must be considered prolonged (Summary of Product Characteristics (Trisenox)).

- Related to hepatotoxicity: increase in serum bilirubin and/or SGOT and/or SGPT and/or alkaline phosphatase,
- Related to Hematological toxicity. This drug may induce severe and prolonged myelosuppression with subsequent anemia, neutropenia, thrombocytopenia. Less frequently hyperleucocytosis or leucopenia have been reported.
- Related to general tolerance (fever, chills, fatigue, bleeding, edema...)
- Related to immunosuppression such as infectious complications (candidosis, herpes-zoster, pneumonia, bacteremia, septicemia, septic choc...),
- Related to digestive toxicity (nausea, vomiting, diarrhea...),
- Related to metabolism disorders (hyperglycemia, hypokalemia, hypomagnesaemia...),
- Renal insufficiency,
- Related to nervous system (paraesthesia, dizziness, headache...),
- Related to eye disorder (vision blurred),
- Related to cutaneous tissues (prurit, rash...),
- Related to musculoskeletal, connective tissue and bone disorders (myalgia, arthralgia, bone pain...).
- Related to pulmonary disorders (dyspnea,,,)

All AE not previously described in the Summary of Product Characteristics of TRISENOX® or in the Investigator Brochure of ARSCIMED® should be considered as unexpected AE.

### **11.9. Safety Committee**

An independent safety committee (including experts in the field) will be established by the sponsor to assess at regular intervals the progress of the trial, the safety data, and the critical efficacy endpoints, and to recommend to the sponsor whether to continue, modify, or stop the trial.

During the study, meetings of the Independent Data Monitoring Committee will be organized periodically.

### **11.10. Annual Safety Report**

A safety report will be produced annually. The “Development International Birth Date” (DIBD) is used to determine the start of the annual period for the Annual Safety report (ASR). This date is the sponsor’s first authorization to conduct a clinical trial in any country worldwide. The start of the annual period for the ASR is the month and date of the DIBD. The start of the annual period for the ASR is the month and date of the DIBD. The data lock point of the ASR can be designated as the last day of the month prior to the month of the DIBD.

This report will be prepared by the sponsor according to the current ICH guideline E2F on development safety update report. Additionally, the two following listings will be provided: Interval line listings of the Serious Adverse Reactions (SARs) that were reported to the sponsor during the period covered by the ASR; and Cumulative summary tabulations of serious adverse events that have been reported to the sponsor since the DIBD.

This report will be submitted to the competent authorities and to the ethics committees by the sponsor within 60 days from the above anniversary date.

In addition, an independent data safety committee will be constituted to assist the sponsor (please see Section 11.9).

## **12. Quality Control**

### **12.1. Good Clinical Practice**

The study will be performed according to the Guidelines for Good Clinical Practice (ICH Harmonized Tripartite Guideline for Good Clinical Practice, (17.01.1997)).

The investigator will be thoroughly familiar with the appropriate use of the study drug as described in the protocol and SPC. Essential clinical documents will be maintained to demonstrate the validity of the study and the integrity of the data collected. A trial master file should be established at the beginning of the study, maintained for the duration of the study and retained according to the appropriate regulations.

### **12.2. Auditing**

To guarantee a high quality of treatment for the patients within the present study, the sponsor will insure that the participating centres fulfill the following criteria:

- fulfilling of legal requirements
- experience of the principle investigator of the entire study and the respective centre with respect to study conduct
- International Conference on Harmonization (ICH)/GCP knowledge and certifications

### **12.3. Monitoring**

Regular monitoring is an essential part of the study conduct. It will be performed by the Sponsor of the study. After the initiation visit, the frequency of monitoring visits will depend on the course of the study, and recruitment. It is the monitor's responsibility to make the local investigators and all the staff who is involved into the study or the care of the patients familiar with the protocol.

During the course of the study, the monitor will control the progress of the study, the commitment to the protocol, the documentation and careful usage of the study medication, and the maintenance of GCP guidelines and legal obligations. Problems as well as changes in reported data will be worked out in collaboration with the local investigator, who is obliged to cooperate with the monitor and to allow access to the patients' charts. Source data verification is performed by the monitor. This protocol is classified as a “D” risk level estimated for the patients (Phase II= very high risk predictable).

Inclusion criteria will be verified in 100% of patients. The monitor will have to respect that the data she/he comes into contact with are highly confidential. A monitoring report will be provided for each visit.

